# 5. Screening and Consent

# 5.1. Screening

All trial activity must be recorded in the patient's NHS medical notes in each of the pathways. It is important that a record of the consultation, trial information and eligibility reviews are documented in the patient's medical notes and each entry dated and signed by the individual completing the activity.

## Screening data

Sites will be required to provide a summary of screening data on an ongoing basis during the recruitment period, which will be reviewed regularly by the Trial Management Group (TMG) and oversight committees.

## 5.2. Consent

Written informed consent for each participant must be obtained prior to performing any trial related procedure.

The potential participant will be given the opportunity to ask questions throughout the process. Consent will be obtained by a member of the research team in accordance with the delegation of responsibilities authorised by the Principal Investigator on the site delegation log. This will usually be by a medically qualified doctor, or where local Trust policy allows this may be a research nurse. **Eligibility for the trial must always be confirmed by a medically qualified doctor using the eligibility checklist.** 

Consent for the trial will be taken in writing. In light of the COVID-19 pandemic, alternative methods (e.g. remote consent) may be used where a baseline face-to-face visit is not possible; local NHS policy will dictate the method of consultation/visit and all consent taking will be in accordance with trial approvals, applicable regulatory policies and NHS guidelines.

All patients identified as being potentially eligible for the trial will be given a Participant Information Sheet (PIS) and a member of the site research team will explain the trial to the patient. Where a face-to-face visit is not possible e.g., due to social distancing measures, a copy of the PIS may be posted or provided electronically, whichever is convenient to the patient. The potential participant will also be given contact details so that they can ask any questions they may have. A signed consent form must be sent electronically or via post to the clinical team.

The consent documentation will also inform participants that their General Practitioner (GP) will be made aware of their participation in the trial.

# 5.2.1. Responsibilities

It remains the responsibility of the Principal Investigator to ensure informed consent is obtained appropriately. A Participant Information Sheet (PIS) will be provided to facilitate this process. Investigators or "delegate(s)" will ensure that they adequately explain the aim, trial treatment, anticipated benefits, and potential hazards of taking part in the trial to the participant. They will also stress that participation is voluntary. Any potential participant is free to decline participation and may withdraw from the trial at any time. Every potential participant should be given 24 hours to

Trial	TB-DILI Trial	Protocol	1.2	date:	02-Aug-2022	Page 23 of 58
name:		version:				

read the PIS and, if they wish, to discuss their participation with others, such as family members, their GP or other healthcare professionals outside of the site research team.

## 5.2.2. Obtaining consent

Patients who are identified as being potentially eligible for the trial will be asked by the investigator or delegate if they are interested in participating and will be given a copy of the PIS to read. Patients attending a consultation by telephone or video call, will be given the same information about the trial and if interested, sent a copy of the PIS by post or electronically. The PIS will also be available online.

If a patient expresses an interest in participating in the trial, they will be asked to sign and date the latest version of the informed consent form (ICF). Details of the trial and the participants participation including date of consent should be recorded in the medical notes.

The participant must give explicit consent for the regulatory authorities, members of the research team and representatives of the Sponsor to be given direct access to the participant's medical records, and a copy of the signed ICF to be sent to the Nottingham Clinical Trials Unit (NCTU).

The consent form will include consent for the collection of contact details for the purpose of obtaining follow-up information and receiving trial communications.

The Investigator or delegate will then sign and date the form. Copies of consent forms should be filed in the participant's medical notes (where medical notes are electronic, a copy must be scanned (where paper) and uploaded into the patient's notes, or digitally uploaded (where electronic)), and the original kept in the Investigator Site File (ISF). Once the participant is enrolled onto the trial, the participant's unique trial identification number will be entered on the ICF maintained in the ISF.

Throughout the trial, the participant will have the opportunity to ask questions. Any new information that may be relevant to the participant's continued participation will be provided. Where new information becomes available which may affect a participant's decision to continue, the participant will be given time to consider this and if they are happy to continue will be re-consented. Re-consent will be documented in the medical notes. The participant's right to withdraw from the trial will remain.

Electronic copies of the PIS and ICF will be available from the NCTU and via the trial website. It is the responsibility of the local site research team to ensure that all copies available locally are printed or copied onto the headed paper of the local institution.

#### 5.3. Optional consent for sub-study

Potential participants who do not enter the trial will be approached for consent to use their routinely collected data. These data will complement results from the main trial and provide additional valuable data on DILI occurrence and recurrence.

Documentation of consent will be the same as outlined in section 5.2.2

Trial	TB-DILI Trial	Protocol	1.2	date:	02-Aug-2022	Page 24 of 58
name:		version:				

# 5.4. GP Notification

Following randomisation and with the participant's consent, their GP will be informed that the participant is taking part in the trial.

Trial	TB-DILI Trial	Protocol	1.2	date:	02-Aug-2022	Page 25 of 58
name:		version:				

# 6. Enrolment and Randomisation

# 6.1. Enrolment

Following informed consent, baseline data will be collected by a member of the site research team and the participant will be enrolled using the secure online trial database. Further information on baseline data collection requirements is detailed in section 8.2.

An authorised member of the site research team will log into the secure randomisation system and randomise the participant.

## 6.2. Randomisation

Eligible patients will be individually randomised on a 1:1 ratio to one of the treatment groups using an online randomisation system developed and maintained by the NCTU. Access to the system will be granted by the NCTU in accordance with the roles delegated by the Principal Investigator on the Site Delegation Log.

Treatment will be assigned using a minimisation algorithm balancing on the following factors:

- Recruitment site
- Participant's age ( $\leq$  35 and >35 years)
- Participant's worst severity of DILI up to randomisation (mild and moderate/severe)

The randomisation algorithm will include a probabilistic element to allocation making prediction of the allocated group virtually impossible.

#### 6.3. Blinding and concealment

Allocation will be concealed to trial staff prior to randomisation using REDCap, an automated web system operated by the NCTU.

Blinding of the participants and site research team following randomisation is not possible due to the nature of the interventions.

Table 3 provides an overview of the blinding status of all individuals involved in the management and delivery of the trial.

Trial role	Blinding status	Comments
Participant	Not blinded	Not possible due to the nature of the intervention.
		Participants will be informed
		which arm of the trial they
		have been randomised to
		immediately after
		randomisation.

#### Table 3: The blinding status of individuals involved in the trial

Trial	TB-DILI Trial	Protocol	1.2	date:	02-Aug-2022	Page 26 of 58
name:		version:				

Trial role	Blinding status	Comments
Principal investigator and site research staff	Not blinded	Not possible due to the nature of the intervention. Following randomisation, an e-mail will be sent to the PI (unblinded for participants they PI randomise only) and/or member of the site research team performing the randomisation (as delegated) confirming treatment
Chief Investigators	Blinded	allocation.The Chief investigator and Deputy Chief investigator will remain blinded to treatment allocation overall (knowledge of treatment allocation is limited to participants at their own site). In instances where serious adverse events are reported, the CIs will become unblinded to complete the full causality assessment.
Adjudication Panel	Blinded	The adjudication panel will remain blinded to treatment allocation overall when performing adjudication for a potential DILI during various timepoints within the trial.
Software programmer	Not blinded	The software programmer is responsible for the management of the randomisation system and database and will have access to all unblinded datasets within both systems.
TB-DILI Trial Management staff within NCTU	Not blinded	
 
Blinding of trial Management staff within NCTU impractical due to the range of potentially unblinding data collected during the trial.
 
For example, Serious Adverse Event reports will be handled by the trial management team who may become unblinded to a participant's treatment allocation.
 

ſ	Trial	TB-DILI Trial	Protocol	1.2	date:	02-Aug-2022	Page 27 of 58
	name:		version:				

Blinding status Not blinded	Data management staff will
	have access to the unblinded
	datasets within the trial
	randomisation system and
	database to ensure data
	quality and undertake central
	monitoring activities.
Not Blinded	The trial statistician will
	remain blinded (they will not
	have access to treatment
	allocations or data which has
	the potential to unblind) prior
	to approval of the statistician
	analysis plan. After approval of
	the analysis plan the trial
	statistician will be able to
	access potentially unblinding
	data. They will also be able to
	request treatment allocation
	data where necessary (e.g. for
	the purposes of preparing
	interim reports).
Blinded	Where possible the senior trial
	statistician will remain blinded
	and not have access to
	treatment allocations or data
	which has the potential to
	unblind until after the final
	database lock.
Not blinded	A statistician independent of
	the trial management team
	will be responsible for
	validating statistical analysis
	and will therefore be
	unblinded to trial
	interventions.
Blinded	The health economist will not
	have access to treatment
	allocations or data which has
	the potential to unblind until
	after the final database lock.
	Blinded

Trial	TB-DILI Trial	Protocol	1.2	date:	02-Aug-2022	Page 28 of 58
name:		version:				

# 7. Trial treatment / intervention

# 7.1. Treatment

Patients will be randomised to one of the following treatment arms:

ARM	TREATMENT	FORMULATION AND DOSE
CONTROL	EHRZ	See NICE Guideline (standard dosing as per BNF Guidelines)
INTERVENTION	EHR	See ATS TB Guideline (standard dosing as per BNF Guidelines)

# 7.2. Treatment Supply and Storage

## 7.2.1. Treatment Supplies

Following randomisation and treatment allocation, trial treatment will be dispensed to participants from standard clinical stocks in accordance with the usual site supply procedures.

## 7.2.2. Packaging and Labelling

Trial specific labelling will not be required as all IMPs have a marketing authorisation in the UK and are being used within their licensed indication.

The IMP will be dispensed to a trial participant in accordance with a prescription given by an authorised healthcare professional and labelled in accordance with the requirements of Schedule 5 to the Medicines for Human Use (SI 1994/31 94) Marketing Authorisations Etc. Regulations 1994 that apply in relation to relevant dispensed medicinal products.

# 7.2.3. Storage of Treatment

There are no trial-specific requirements for the storage of any of the IMPs used in this trial. All treatment prescribed and dispensed for the purpose of the trial will originate from standard clinic stock which will be stored in accordance with the manufacturer's storage instructions as detailed in the applicable Summary of Product Characteristics (SmPC). Sites will follow their own local policies for storage of medication.

# 7.3. Dosing Schedule

In accordance with standard practice, participants will be instructed to start their allocated treatment on the day they receive their treatment, this will be 1-3 days from the date of randomisation. Start and stop dates of medication will be included in the eCRF.

#### 7.4. Accountability Procedures

Sites will follow their own local procedures for recording medication dispensed to trial participants. There are no additional trial-specific accountability requirements.

Trial	TB-DILI Trial	Protocol	1.2	date:	02-Aug-2022	Page 29 of 58
name:		version:				

#### 7.5. Treatment Modification

#### 7.5.1. Missed Doses

In the case of any missed doses, participants will be advised to continue their treatment course until it is completed. If the clinician feels too many doses have been missed then treatment will be restarted. This is in line with standard care. Information on compliance with allocated treatment will be collected in the eCRF.

#### 7.5.2.Adherence

For the purposes of assessing adherence to the interventions in the internal pilot, adherence will be defined as treatment prescription consistent with randomised allocation. For participants for whom treatment is prematurely stopped or modified because of a suspected DILI recurrence, then these cases will be reviewed to ascertain adherence to randomised allocation up until the point of DILI recurrence.

# 8. Trial procedures and assessments

#### 8.1. Summary of assessments

A summary of trial procedures is shown in figure 2. A detailed description of each procedure can be found in section 8.2.

Figure 2: Summary of trial procedures time point

Trial	TB-DILI Trial	Protocol	1.2	date:	02-Aug-2022	Page 30 of 58
name:		version:				

															TRIAI	L PERI	OD						
TIMEPOINTS	E	R	Pha	ise A						Pha	se B				Phase	e C		DIL	Recurrence		ЕоТ		Follow- up Post R
Timepoint [Weeks]	W-2	W-1				W0				W1	W2	W4	W6	W8	W16	W24	W32	Diagnosis	2-Weeks after	W25	W33	*	W52
Timepoint [Days]		-1	0	1	3	4	6	7	9									of DILI	treatment re-start				
Tolerance [Days]	а	±2	±1	±1	±1	±1	±1	±1	±1	±4	±4	±4	±4	±4	±14	±14	±14	-	-	-	-		-
ENROLMENT:																							
Eligibility screen	Х																						
Informed consent	Х																						
Baseline Assessments																							
Adjudication panel confirmation	Х																	Х					
EQ-5D-5L	Х																						
Randomisation		Х																					
CONTROL ARM																							
Drug Re-Introdcution																							
Reintroduce EH				Х																			
Reintroduce R						Х																	
Reintroduce Z								Х															
Drug Discontinuation																							
Discontinue Z+R														Х									
Assessments																							
LFT (suggested not mandated)			х		х		х		х	х	х	x	x	x	x	x	x	х	х				
EQ-5D-5L			Х								Х							Х	Х	Х			Х
Follow-Up post EoT																							
Follow-up telephone call																				Х		Х	
INTERVENTION ARM																							
Drug Re-Introdcution																							
Reintroduce EH				Х																			
Reintroduce R						Х																	
Drug Discontinuation																							
Discontinue R														Х									
Assessments																							
EQ.5D-5L			Х						_	Γ.	Х							Х	Х		Х		Х
Follow-Up post EoT						CI 31				_					 								
Follow-up telephone call					ľ	5.510	[														Х	Х	

E = Enrolment

R = Randomisation

EoT = End of Treatment

a. The enrolment period will occur at the onset of DILI, the period between E & R will be variable dependent upon patient recovery. Predicted average time is 2 weeks

\* Every 12 weeks after EoT until 12 months post R

Trial	TB-DILI Trial	Protocol	1.2	date:	02-Aug-2022	Page 32 of 58
name:		version:				

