# 1.2.3. Choice of treatment

Both regimens are accepted as standard of care in the NHS and globally. Based on weak evidence, one regimen may be associated with a lower DILI recurrence frequency but entails a longer total duration of treatment (9 months vs 6 months).

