#### EoT

• EQ5D questionnaire is completed one week after the end of treatment: This is expected to be W25 for control arm and W37 for intervention arm

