## 11.5. Data sharing

Individual participant medical information obtained as a result of this trial is considered confidential and disclosure to third parties is prohibited with the exceptions noted in this protocol.

Participants' contact details, including name, address, telephone/mobile number and email will be shared between participating sites and NCTU for the purposes of follow up, issuing questionnaires and electronic reminders (text/email) for the trial. The University of Nottingham's approved provided of SMS texting services eSendex (https://www.esendex.co.uk/) will be used to message participants. This means that participants mobile numbers will be shared with eSendex via a secure data transfer in order to run the service, and all appropriate security steps are taken to ensure the confidentiality and protection of the data in their care. Participants have an optional consent to have there information held by essendex in order to be contacted via text message.

Any personal data will be held in a secure database using encryption, with restricted password protected access. Only appropriate members of the participating site team and NCTU research team will have access to these data.

Participant confidentiality will be further ensured by utilising identification code numbers to correspond to treatment data in computer files.

Data generated as a result of this trial will be available for inspection on request by the sponsor local R&D departments and the NCTU.

Anonymised participant data may be shared with researchers external to the trial research team in accordance with the NCTU's data sharing procedure. All requests for data should be sent to the NCTU.

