# 15. Health Economics

Quality of Life will be measured using an online questionnaire to collect EQ-5D-5L data, with patients prompted by email / text message, and/or telephone. Patients who cannot use the online system will provide information by telephone

Quality of Life will be measured at 5 junctures for all participants: i) during initial DILI, ii) after DILI recovery prior to start of ATT, iii) 2 weeks after starting ATT, iv) one week after the end of ATT and v) at 12 months post-randomisation (the primary outcome). Participants with a DILI recurrence will have 2 additional measurements, vi) during DILI recurrence and vii) after recovery from DILI recurrence when on ATT. This is to enable assessment of the QoL impact of initial DILI (against a background of QoL detriment due to active TB and ATT, comparing i and ii), recurrent DILI (comparing vi and vii), TB disease under treatment (comparing ii and iii), and ATT (comparing iii and iv, and iii and v). The two arms of the trial will be compared using measurements i and v.

To enable healthcare resource costs to be calculated based on staff costs (determined by time and grade), drugs costs (from the British National Formulary), and costs of tests (NHS tariffs), we will record information on health services used by participants relevant to TB care during treatment and follow-up. This will include clinic visits, home visits, additional drugs used, and additional clinical resources required to manage recovery from DILI (e.g. ICU care). Relevance of services used to TB care will be determined by the attending TB team.

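### Figure 2 schedules the intervention arm's end-of-treatment EQ-5D-5L at W33, four weeks before the W37 given in section 9.1.4

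*Protocol*

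**What the plan says.** - **Figure 2, section 8.1.** The later week headers run "W16 W24 W32 Diagnosis 2-Weeks after W25 W33", followed by an asterisk column and W52. Control's end-of-treatment EQ-5D-5L and telephone call are marked under W25. The intervention arm's are marked under W33. The tolerance row has a dash for both end-of-treatment columns.
- **Section 9.1.4, EoT.** The EQ-5D is due a week after treatment ends, and the text adds: "This is expected to be W25 for control arm and W37 for intervention arm".
- **Section 1.2.3.** The regimen that may have fewer recurrences "entails a longer total duration of treatment (9 months vs 6 months"). Section 1.2 also describes a 9-month course without pyrazinamide.
- **Section 15.** Reading iv is taken "one week after the end of ATT". The quality-of-life effect of treatment is assessed as "ATT (comparing iii and iv, and iii and v"). The arms are compared on readings i and v.

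**The concern.** Figure 2 is the schedule that sites and the trials unit are likely to work from, and for one arm it gives a different week from the text. Section 8.1 sends the reader to a section 8.2 for details, but the contents list goes from 8.1 straight to 9, so someone using the figure is not led to the W37 statement.

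What is at stake is reading iv. It is meant to be taken off treatment, so that setting it against reading iii (two weeks after restarting) shows the burden of the drugs. Section 15 says the EQ-5D-5L is collected online, "with patients prompted by email / text message, and/or telephone", and section 11.5 has contact details shared "for the purposes of follow up, issuing questionnaires and electronic reminders (text/email) for the trial". The protocol does not say whether a prompt is triggered by the recorded stop date or by a scheduled week. If it is a scheduled week taken from Figure 2, intervention participants are asked while still on treatment. Control participants would not be, on the month length that the printed weeks imply. The error would therefore fall on one arm only.

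**Working it through.** **Inputs.** Figure 2: control W25, intervention W33. Section 9.1.4: control W25, intervention W37. Section 1.2.3: 6 and 9 months. Section 9.1.4, 12 Months Post Randomisation: a window of 28 days either side. Section 7.3: treatment starts 1 to 3 days after randomisation.

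**Column check.** Counting the columns of Figure 2, the control EQ-5D-5L and call fall under W25 and the intervention EQ-5D-5L and call under W33. W33 is unlikely to be a misread digit: it is the last treatment-phase column plus one (32 + 1), just as W25 is 24 + 1.

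**Reproducing the printed weeks.** Take week = 4 × months + 1.

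| Course | Week | Where printed |
|---|---|---|
| 6 months | 6 × 4 + 1 = 25 | control, figure and text |
| 9 months | 9 × 4 + 1 = 37 | intervention, text |
| 8 months | 8 × 4 + 1 = 33 | intervention, figure |

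The rule reproduces control in both places and intervention in the text. It does not reproduce W33 for a 9-month course.

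**Do calendar months rescue W33?** The arms differ by 9 − 6 = 3 months, which is 12 weeks on 4-week months or 3 × 30.44 / 7 = 13.0 weeks on calendar months. The text has them 37 − 25 = 12 weeks apart. The figure has them 33 − 25 = 8 weeks apart, which fits neither.

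**Size of the mismatch.** (37 − 33) × 7 = 28 days for intervention and (25 − 25) × 7 = 0 for control, whatever the month length. Figure 2 gives no tolerance for these columns, and its widest tolerance elsewhere, 14 days either side, is half the gap.

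**Position relative to the last dose.** W25 is day 175, W33 day 231 and W37 day 259.

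| | 4-week months | Calendar months (30.44 days) |
|---|---|---|
| Intervention last dose | day 252 | about day 274 |
| W33 | 21 days before | about 43 days before |
| W37 | 7 days after | about 15 days before |
| Control last dose | day 168 | about day 183 |
| W25 | 7 days after | about 8 days before |

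Only 4-week months put control's W25 and intervention's W37 a week after the last dose, so the printed weeks appear to use that convention.

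**Is reading v safe?** The earliest is day 364 − 28 = 336. On calendar months that is 336 − 274 = 62 days after the last dose, or 59 if treatment starts 3 days after randomisation. The iii-versus-v contrast therefore remains on- against off-treatment.

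**The case against.** The case for leaving this alone is that the weeks are nominal labels for an event-driven assessment. Sections 9.1.4 and 15 both state the rule in terms of the end of treatment, the figure's columns sit under an end-of-treatment heading, and section 9.1.4 calls its weeks expected. Missed doses and restarts (section 7.5.1) will move the real date from patient to patient. Section 7.3 says "Start and stop dates of medication will be included in the eCRF", so prompts can be tied to the actual date. Section 9.1.4 gives a week for the EQ-5D only, so the telephone call is not directly contradicted. On calendar months W37 is itself early. Finally, changing W33 alone breaks the figure's pattern of following W24 with W25 and W32 with W33.

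Much of this stands, and it is why the point is minor. The rule is right, and the harm depends on how prompts are set up. The direct contradiction concerns the EQ-5D; for the call it is an inference from the end-of-treatment heading. Stop dates would also let mistimed readings be identified later, although a post-treatment reading that was never taken could not be recovered.

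Two parts do not stand. Approximate labels do not explain why the text and the figure agree for control and differ by four weeks for intervention. Nor does the visit pattern matter: in Figure 2 the treatment-phase columns from W16 to W32 carry only liver function tests marked as suggested, so no fixed visit has to precede the end-of-treatment column.

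**Conclusion.** The inconsistency is real, and W33 is the value to correct. It is 28 days earlier than the text in the intervention arm only, and would place reading iv 21 days (4-week months) to about 43 days (calendar months) before the last dose. If prompts follow the figure, the iii-versus-iv contrast in that arm compares two on-treatment readings. The primary outcome, the sample size, the between-arm comparison on readings i and v, and the iii-versus-v contrast are unaffected. Severity is minor.

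The choice of W37 over W33 assumes that the full course is counted from reintroduction. The protocol does not say whether treatment before the liver injury counts. Control's W25 implies that it does not, and an equal credit in both arms would move control off W25 as well.

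**What to change.** In Figure 2, change the intervention arm's end-of-treatment week from W33 to W37. Add a footnote there that end-of-treatment assessments fall due one week after the actual last dose, with the printed weeks as expected values only. The footnote holds whichever month length is meant and covers the telephone call as well. The treatment-phase visits can stay as they are. The cost is one cell and one note at the next amendment, with no extra patients, visits or analyses.
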